The second aim is to demonstrate the safety and tolerability of NAC when combined with ALC. Physiological responses (e.g., heart rate) and breath alcohol levels will be measured throughout each experimental session. Adverse events will also be assessed across each maintenance period in order to demonstrate that NAC can safely be administered to subjects with AUD.

A third, exploratory, aim is to evaluate potential mechanisms contributing to the influence of NAC on the pharmacodynamic effects of ALC. To this end, a number of validated trait measures (e.g., the Zuckerman-Kuhlman Personality Questionnaire, the Barratt Impulsivity Scale) and cognitive-behavioral tasks (e.g., Go/Stop Task, Alcohol Delay Discounting Task) will be completed. Outcomes from these measures will be correlated with pharmacodynamic and safety/tolerability outcomes.

The research proposed here will directly translate findings from preclinical research and provide the initial prospective clinical evidence that restoration of glutamate homeostasis with NAC has promise for treating AUD. This study will also provide basic science information about the glutamatergic mechanisms

Behavioral Effects of Drugs: Inpatient (34) (Alcohol and N-Acetylcysteine) (PI: [name].)
underlying the pharmacodynamic effects of ALC in humans. Overall, the proposed research seeks to expand the scope of current AUD treatment research by focusing on glutamate homeostasis, which has strong preclinical evidence supporting its critical role in AUD but remains unstudied in clinical research.

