4. STUDY POPULATION

Up to 150 individuals will be screened to participate in this study. We intend to enroll 25 (17 male and 8 female) completers into the study. Screening procedures will be conducted under our lab's screening protocol (03-0509). Inclusion and exclusion criteria are outlined below.

Inclusion/Exclusion Criteria

The following criteria must be met for an individual to participate in the study: 1) able to speak/read English; 2) not seeking treatment at the time of the study; 3) female or male between the ages of 21 and 55 years; 4) one binge drinking episode (5+/4+ standard alcoholic drinks per drinking session for men and women, respectively) in the past 30 days; 5) recent ALC use verified by ethyl glucuronide positive urine, as well as fulfillment of DSM-5 diagnostic criteria for AUD; 6) other than the diagnosis for AUD at the time of the interview, subjects must be otherwise healthy; 7) ECG, read by cardiologist, within normal limits; 8) body mass index of 19-35; 9) females using an effective form of birth control and not pregnant or breast feeding; 10) judged by the medical staff to be psychiatrically and physically healthy; 11) able to abstain from ALC for 12 hours prior to session; and 12) no contraindications/allergies to NAC or ALC. Potential research subjects who are seeking treatment for substance abuse/dependence will be excluded from research participation, and will be referred to an appropriate treatment program.

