Safety and Tolerability Measures. Physiological measures (i.e., BAL measurements, heart rate and blood pressure) will be recorded upon arrival at the LHBP, before ALC administration and throughout the session at the intervals noted in Table 2 using digital monitors. ALC will not be administered if a subject's heart rate is ≥ 100 bpm, systolic pressure is ≥ 150 mmHg or diastolic pressure is ≥ 100 mmHg. A subject will be excluded from further participation if he/she exhibits hypersensitivity (i.e., heart rate > 130 bpm, systolic pressure > 180 mmHg, diastolic pressure > 120 mmHg) during maintenance on NAC and/or to the effects of ALC. The UKU Side Effects Rating Scale will be completed at the end of sessions (Lingjaerde et al., 1987).

Trait Questionnaires and Cognitive Behavioral Tasks. To explore potential mechanisms of NAC effects, subjects will complete a battery of trait measures at screening that assess various aspects of personality, including the Zuckerman-Kuhlman Personality Questionnaire, the Barratt Impulsiveness Scale and the Snaith-Hamilton Pleasure Scale (Patton et al., 1995; Snaith et al., 1995; Zuckerman and Kuhlman, 2000). As outlined in Table 2, subjects will also complete the Commodity Purchase Task, n-back Task, the Go/Stop Task and Money and Alcohol and Money Delay Discounting Tasks. These specific tasks measure several key facets of alcohol-related decision-making and impulsivity (MacKillop, 2016; Reynolds et al., 2008) and, along with the self-administration and subjective effects outcomes described above, model key stages of the addiction cycle (Litten et al., 2016b; MacKillop, 2016).

Commodity Purchase Tasks (Appendix A). Commodity tasks will be used to assess economic demand for alcohol and soda (Amlung et al., 2015; Bruner and Johnson, 2014; Murphy and MacKillop, 2006; Strickland and [name], 2017). In these task subjects are asked to indicate the hypothetical number of items

Behavioral Effects of Drugs: Inpatient (34) (Alcohol and N-Acetylcysteine) (PI: [name].) (e.g., one alcoholic drink) they would purchase at a range of monetary increments (e.g., \$0.00 [free] to \$15/drink). All choices are hypothetical and will not be purchased or administered. Data from the commodity purchase task will be analyzed using economic demand equations previously applied to purchase task data (e.g., Strickland et al., 2016). Primary outcomes of this task include elasticity of demand (α) and intensity of demand (Q_0).

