Data will be analyzed as raw scores. Statistical significance refers to $p < .05$. Number of Drinks Chosen on the ALC self-administration procedure will be analyzed with a one-factor, repeated-measure ANOVA with NAC dose (0, 1.2 and 2.4 g/day) as the factor. A significant attenuation (i.e., decreased ALC self-administration) will be inferred if the main effect of NAC attains statistical significance in the ANOVA. Tukey’s HSD *post-hoc* test will be used to make appropriate pair-wise comparisons between means if the ANOVA outcome attains statistical significance. Data from the subjective-effects questionnaires and safety/tolerability measures following administration of the sampling dose will be calculated as peak effect (i.e., the maximum score observed after ALC sampling). These data will be analyzed in the same fashion as ALC self-administration data. The influence of relevant biological (e.g., age) and behavioral variables (e.g., cigarette smoking, weekly ALC use) will be determined in initial correlation analyses and included as covariates in analyses should they be significantly associated with outcomes. Outcomes from trait questionnaires and cognitive behavioral tasks will also be correlated with self-administration, subjective effect and physiological data to explore the mechanisms by which NAC attenuates the effects of ALC.

Power and Sample Size Considerations. We used the results of a prior meta-analysis of human laboratory studies of ALC self-administration and craving to determine an appropriate sample size for the present experiment (Hendershot et al., 2016). That meta-analysis demonstrated that naltrexone maintenance decreased the quantity of ALC consumed and self-reported craving relative to placebo with an average estimated effect size (i.e., Cohen’s f) of approximately 0.27. Considering the overall design and use of three NAC doses, enrolling 25 subjects will provide sufficient power (power = 0.80, $\alpha = 0.05$, G*Power) to detect a medium effect size (f) of approximately 0.26 for attenuation of the effects of ALC as a function of NAC dose.

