17. DATA AND SAFETY MONITORING

Data Monitoring Plan. Data will be collected using a computerized data collection and management system. This system automates the collection of the subjective-effect and physiological data, which ensures the accuracy and completeness of data collection. The data are stored in a unique file on the hard drive of the computer and are printed after all the tasks are completed. Paper-and-pencil task data are verified by staff and double-entered into excel spreadsheets after each session. In all instances, the data files do not contain the name of the subject; but instead, a unique four-digit number identifies each subject. A computer file linking the unique number with the subject's name will be kept on a stand-alone, password-protected computer. Data files for experimental tasks and physiological measures from each experimental session will be manipulated and combined into a single electronic spreadsheet for each subject by the PI. Data for all subjects will then be combined into a single electronic spreadsheet and separated by experimental measure for statistical analysis using SPSS (IBM Corporation, Armonk, NY).

The primary outcome for this study will be Number of Drinks during ALC self-administration. Secondary outcome measures will include craving, BALs, physiological and subjective response to ALC, self-reported ALC use in the natural environment during maintenance, as well as performance on cognitive-behavioral tasks, and the Udvalg for Kliniske Undersøgelser (UKU) Side Effects Rating Scale.

As noted above, the majority of data are collected using an automated computer system, which increases the accuracy and completeness of data collection and ensures the validity and integrity of the data. Hand written questionnaires and tasks are double-entered and verified by staff prior to analysis. The initial data manipulation described above will be conducted twice and compared. The quality of manipulated data and data analyses will be monitored by random inspection by the PI and/or Co-Investigators.

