Safety Monitoring Plan. Potential subjects will provide information regarding their ALC and drug use history and undergo an extensive physical and psychiatric health screening to determine their eligibility and safety of their participation. Potential subjects must meet DSM-5 criteria for AUD and must present with a urine sample positive for ethyl glucuronide at the time of screening. Any potential subject with a history of clinically significant physical disease, current physical disease (e.g., impaired cardiovascular functioning, histories of seizure, head trauma or CNS tumors), or current or past histories of psychiatric disorder, other than AUD or tobacco use disorder, will be excluded from research participation. Females must be using an effective form of birth control in order to participate and must not be pregnant. Methods for monitoring AEs will include observations by the medical and research staff, spontaneous report by the subjects, regular measurement of cardiovascular indices and use of the UKU Side Effects Rating Scale and subjective-effects questionnaires. Subjects will not receive study drug if they have any signs or symptoms that may contraindicate its administration (e.g., heart rate and blood pressure outside of predetermined range).

All AEs occurring during the course of the study will be collected, documented and reported to the PI. The occurrence of AEs will be assessed daily for the duration of participation and during the follow-up visits at 2 and 4 weeks following discharge. Each week a study investigator will review the AE forms from the previous week for events that were reported as new or continuing. The study investigators will follow all AEs to the point of a satisfactory resolution. Subjects may be withdrawn from the study if the medically responsible investigator determines it is the best decision in order to protect the safety of the subject. All AEs will be assessed to determine if they meet criteria for a serious AE.

Serious AEs, as defined by the FDA, will be systematically evaluated daily for the duration of participation and during the follow-up visits at 2 and 4 weeks following discharge. Any serious AE, whether or not related to the study drug, will be reported to the IRB, NIAAA, and the FDA. The initial serious AE report will be followed by submission of a completed serious AE report to all three institutions.

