In the event that a subject either withdraws from the study or the investigator decides to discontinue a subject due to a serious AE, the subject will have appropriate follow-up medical monitoring. Monitoring will continue until the problem requiring hospitalization has resolved or stabilized with no further change expected, is clearly unrelated to the study medications, or results in death. Outcome of serious AEs will be

Behavioral Effects of Drugs: Inpatient (34) (Alcohol and N-Acetylcysteine) (PI: [name].) periodically reported to NIAAA. A summary of the serious AEs that occurred during the previous year will be included in the annual progress report to NIAAA.

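### The planned safety analysis compares session scores only, so adverse events and withdrawals during take-home dosing enter no planned Aim 2 comparison by NAC dose

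*Combined protocol and SAP*

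**What the plan says.** All references are to the combined protocol and SAP.

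- **Aim 2 (Section 1).** The second aim is to show that NAC is safe and tolerated together with alcohol. Adverse events are named as evidence for it: "Adverse events will also be assessed across each maintenance period in order to demonstrate that NAC can safely be administered to subjects with AUD".
- **Analysis (Section 7, Data Analysis).** This is the only safety analysis in the plan. Scores are reduced as follows: "safety/tolerability measures following administration of the sampling dose will be calculated as peak effect (i.e., the maximum score observed after ALC sampling". Then: "These data will be analyzed in the same fashion as ALC self-administration data". That refers to a one-factor repeated-measures ANOVA on NAC dose (0, 1.2 and 2.4 g/day), with Tukey comparisons if the F test is significant at 0.05.
- **Timing (Section 7).** Capsules are taken at home for four full days before each session. On the side-effect scale: "The UKU Side Effects Rating Scale will be completed at the end of sessions".
- **Outcomes (Section 17, Data Monitoring Plan).** "Secondary outcome measures will include craving, BALs, physiological and subjective response to ALC, self-reported ALC use in the natural environment during maintenance". The same sentence goes on to list cognitive-behavioral performance and the UKU scale. Adverse events as such are not listed.
- **Adverse events (Section 17, Safety Monitoring Plan).** "The occurrence of AEs will be assessed daily for the duration of participation", and an investigator reviews them weekly. The only summary described covers serious events: "A summary of the serious AEs that occurred during the previous year will be included in the annual progress report to NIAAA".
- **Sample (Section 4).** "We intend to enroll 25 (17 male and 8 female) completers into the study". Section 7 says that those who complete will have received every dose condition.

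**The concern.** Tolerability problems with an oral drug taken at home tend to appear while it is being taken at home. Section 9 lists nausea, vomiting and diarrhea as common NAC effects, and any of these could lead a subject to stop before the session. The planned comparison looks only at scores from sessions that took place. Under the usual ANOVA, it looks only at subjects who have all three.

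Section 1 says that two active doses are tested to decide which should go forward to a clinical trial. It names effectiveness as the criterion, and Aim 2 supplies the tolerability evidence beside it. If some subjects left because of 2.4 g/day, a comparison among those who stayed could show that dose as no worse than placebo. The information would be in the adverse-event forms, but no planned step carries it into the dose comparison.

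A second weakness lies in the summary measure. Section 9 lists low blood pressure among the less common NAC effects, and blood pressure is to be summarized by its maximum.

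**Working it through.** **1. The plan's own figure.** Section 7 states power of 0.80 with 25 subjects at f of about 0.26 and alpha 0.05. For a one-group within-subject design, lambda = f² × n × m / (1 − rho), with m − 1 and (n − 1)(m − 1) degrees of freedom. Correlation rho = 0.5 and sphericity are assumed, as the plan gives neither.

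- lambda = 0.26² × 25 × 3 / (1 − 0.5) = 0.0676 × 150 = 10.14
- degrees of freedom = 2 and 24 × 2 = 48
- power = 0.795, and the effect detectable with 80% power is f = 0.262

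The stated figure reproduces. It counts 25 subjects with three conditions each. That is consistent with a complete-case analysis but does not establish one, and nothing below depends on it.

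**2. Where each kind of subject is counted.**

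| Subject | Score at that dose | ANOVA as normally run | Mixed model, all sessions held | Table of all dosed subjects |
|---|---|---|---|---|
| Stops during take-home dosing, before the session | None | Subject dropped | Earlier sessions kept | Counted |
| Excluded on vital signs at a first or second session (Section 7) | Exists | Subject dropped, including that score | That score kept | Counted |
| Completes all three sessions | Exists | Used | Used | Counted |

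In the first row no model helps, because the on-dose score does not exist. In the second row the ANOVA discards a score from the very session that led to exclusion.

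**3. Sessions discarded per early leaver.** Take a subject who leaves in the 2.4 g/day condition before its session. Three conditions have 3! = 6 orders. The number of sessions already held is 0 in two orders, 1 in two and 2 in two. If the orders are equally likely (an assumption), the mean is (0 + 0 + 1 + 1 + 2 + 2) / 6 = 1.0. The number of UKU scores at 2.4 g/day is 0 in every order.

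**4. Illustration with assumed rates.** The documents give no intolerance rate. Let q be the share of randomized subjects who leave for intolerance in the 2.4 g/day condition, with no other losses. Then 25 / (1 − q), rounded up, are needed to reach 25 completers.

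| q (assumed) | Randomized | Leavers | Leavers in a three-condition ANOVA | What a by-dose table would show (exact 95% CI) |
|---|---|---|---|---|
| 5% | 27 | 2 | 0 | 2/27 = 7.4% (0.9% to 24.3%) |
| 10% | 28 | 3 | 0 | 3/28 = 10.7% (2.3% to 28.2%) |
| 15% | 30 | 5 | 0 | 5/30 = 16.7% (5.6% to 34.7%) |
| 20% | 32 | 7 | 0 | 7/32 = 21.9% (9.3% to 40.0%) |

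At q = 10% with 28 randomized, the chance of at least one leaver is 1 − 0.9^28 = 0.95, and of three or more 0.54. The intervals are wide, so the table would be descriptive.

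**5. Maximum and low pressure.** Readings are taken at 10, 20 and 30 minutes after the sampling drink and every 30 minutes in the choice blocks. Two series that differ only in one low reading have the same maximum, so a brief dip leaves no trace. A sustained fall lowers every reading, including the maximum, and the ANOVA could detect it.

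**The case against.** The strongest reply is that the plan already gives side effects a comparison by dose. The UKU is a listed secondary outcome, it is named among the methods for monitoring adverse events, and it is analyzed across the three conditions. This is right for everyone who reaches a session, so a reader should not infer that the plan has no side-effect comparison by dose. The gap concerns subjects who miss a session or a condition, and the adverse events themselves.

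It can also be said that no text restricts the safety analysis to completers, and that 25 is an enrollment target. That is fair. The restriction is inferred from how a repeated-measures ANOVA is normally run in SPSS, together with the absence of any stated missing-condition rule.

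Third, adverse events are collected daily, reviewed weekly and followed to resolution. They are not lost from the safety record, and a table by dose could be made afterwards. What stands is that it is not planned, and no rule says who is counted or how stopping is classified.

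Fourth, Section 1 describes NAC as having few side effects, and Section 9 reports earlier use of these doses without serious ones. The loss may therefore be small, and the documents do not show otherwise.

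Two stronger readings are tempting:

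- **Forced re-exposure.** A reader might infer that the rule to repeat a condition after missed doses would oblige someone with a reaction to take the drug again. The Safety Monitoring Plan withholds study drug when contraindicating signs are present and allows medical withdrawal, which largely covers this.
- **No protection against low pressure.** All six limits in Section 7 are upper limits, so a reader might infer that a low reading never stops dosing. The Safety Monitoring Plan withholds drug when heart rate or blood pressure is outside a predetermined range, and a range can have a lower end. The point that remains concerns the analysis summary.

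**Conclusion.** The concern holds in a limited form and should be corrected. Followed as written, the plan gives Aim 2 a dose comparison of session scores among those who reached sessions, and under the usual ANOVA among those with all three. Each subject who stops before a session contributes 0 scores at that dose, and the subject's 0, 1 or 2 earlier sessions are normally discarded as well. Adverse events and withdrawals enter no planned comparison by dose, although Section 1 makes adverse events evidence for the aim. The maximum also misses transient falls in blood pressure.

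This rests on two things: the ANOVA being run in its usual complete-case form, which is an inference, and at least one subject leaving early. The rates of 5% to 20% are assumptions made for illustration. A reader might infer that 2.4 g/day is poorly tolerated, or that the result will be biased by a known amount. The documents support neither. Protection of individual subjects and the primary analysis of drinks chosen are not in question.

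**What to change.** In Section 7, Data Analysis, add text to this effect:

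> The safety analysis will include every subject who took at least one maintenance dose. For each NAC condition we will tabulate the number who started, the number who stopped for a suspected reaction and the number who completed the session, with adverse events by type. Events starting in washout are assigned to the preceding condition, and a repeated condition is counted once per subject. UKU and vital-sign scores will be fitted with a mixed model (NAC dose fixed, subject random) using all sessions held. Minimum systolic pressure after sampling will be reported beside the maximum. The model cannot recover a session that was never held at a dose, so the table is the tolerability result.

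**Cost.** The change needs one reason-for-stopping field, one table and a few sentences. It adds no visit or measurement, and SPSS is already the planned software. An investigator must judge whether a stop was for a suspected reaction. The mixed model assumes that missing sessions are explained by the data observed (missing at random), which is doubtful when a subject leaves because of the dose. That is a further reason to let the table carry the conclusion. The primary analysis does not change.

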8. RESOURCES

This study will take place at University of Kentucky Laboratory of Human Behavioral Pharmacology (LHBP) and the Clinical Services Core (CSC) unit. Study visits will only be conducted on weekdays, but subjects will be provided with emergency contact information should they experience problems/AEs/SAEs on weekends. The LHBP and CSC are well equipped to conduct the necessary physiological monitoring and behavioral assessments. [name] is a psychiatrist who has worked extensively with individuals

Behavioral Effects of Drugs: Inpatient (34) (Alcohol and N-Acetylcysteine) (PI: [name].)

with substance use disorders in both the clinical and research setting and he is the responsible medical investigator for this study. [name] is an adult psychiatrist who has worked extensively with individuals with substance use disorders, especially alcohol use disorder, in both the clinical and research setting and he is the back up medical investigator for this study. They will be available to attend to medical problems as well as any psychological or psychiatric issues that may arise. Drs. [name] will provide scientific oversight for the study and have safely completed numerous human behavioral pharmacology studies. Overall, the study team and resources described above are well equipped to protect subjects and successfully implement, carry out and complete this study protocol.

